9.4.3. Exploratory Analyses

Study JAHH exploratory analyses are summarized in [Table JAHH.4](#). Details of the exploratory analyses will be outlined in the SAP.

Table JAHH.4. Study JAHH Exploratory Analyses

Efficacy/Safety Measures	Variable	Analysis
SLEDAI-2K	Change in proportion of patients who achieve remission of arthritis and/or rash at Week 12	Logistic Regression
28 Tender/Swollen Joint Count	Change in number of joints affected by SLE arthritis at Week 12 and Week 24 compared to baseline	MMRM
	Change in proportion of patients with $\geq 50\%$ reduction in number of joints affected by SLE arthritis at Week 12 and Week 24 compared to baseline	Logistic Regression
CLASI Activity Score	Change at Week 12 and Week 24 compared to baseline	MMRM
	Change in proportion of patients with $\geq 50\%$ reduction at Week 12 and Week 24 compared to baseline	Logistic Regression
Physician Global Assessment of Disease Activity	Change at Week 12 and Week 24 compared to baseline	MMRM
SLEDAI Flare Index (SFI)	Proportion of patients experiencing severe, mild/moderate, or any severity flare	Logistic Regression
	Time to first severe, mild/moderate, or any severity flare	Kaplan-Meier Product Limit
SLICC/ACR Damage Index Score	Change at Week 24 compared to baseline	MMRM
Corticosteroid Sparing	Change in proportion of patients receiving $\geq 10\text{mg/day}$ prednisone at baseline able to reduce prednisone (or equivalent) dose $\leq 7.5\text{ mg/day}$ for 12 consecutive weeks between Week 12 and Week 24	Logistic Regression
Serologic Markers	The difference in reduction of IFN signature between treatment groups at Week 12 and Week 24 compared to baseline	MMRM
	Change in anti-dsDNA level at Week 12 and Week 24 compared to baseline in patients with elevated anti-dsDNA at baseline	MMRM
	Change in C3 and C4 levels at Week 12 and Week 24 compared to baseline in patients with low C3 and C4 at baseline	MMRM

Abbreviations: ACR = American College of Rheumatology; CLASI = Cutaneous Lupus Erythematosus Disease Area and Severity Index; dsDNA = double-stranded deoxyribonucleic acid; IFN = interferon; MMRM = mixed-effects models for repeated measures; SLE = systemic lupus erythematosus; SLEDAI-2K = Systemic Lupus Erythematosus Disease Activity Index 2000; SLICC = Systemic Lupus Erythematosus International Collaborating Clinics.

Note: Additional methods may be used for analysis as deemed appropriate.

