5.1.2. Enrollment Criteria

Entered patients are eligible for enrollment into the study (eligible for randomization) only if they continue to meet all of the entry criteria above, and meet all of the following enrollment criteria at the time of randomization (Visit 2):

Type of Patient and Disease Characteristics

- [6] Have a positive ANA (HEp-2 ANA titer $\geq 1:80$) and/or a positive anti-dsDNA (≥ 30 IU) as assessed by a central laboratory at screening.

Note: The ANA and/or anti-dsDNA measurement may be repeated once within approximately 2 weeks of the initial value, and the value resulting from repeat testing may be accepted for enrollment eligibility if it meets the eligibility criterion.

- [7] Have a SLEDAI-2K score ≥ 4 based on clinical symptoms (not including lab values) at randomization.
- [8] Have active arthritis and/or active rash as defined by the SLEDAI-2K at randomization.

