8.1.2.3. BILAG2004

The BILAG2004 index is a validated global disease activity index designed on the basis of the physician's intention to treat (ITT), focusing on changes in disease manifestations (not present, improving, same, worse, or new) occurring in the last 4 weeks compared with the previous 4 weeks. The instrument assesses 97 clinical signs, symptoms, and laboratory parameters across 9 organ system domains: constitutional, mucocutaneous, neuropsychiatric, musculoskeletal, cardiorespiratory, gastrointestinal, ophthalmic, renal, and hematology. A BILAG A disease activity score is severe disease activity requiring high-dose oral or IV corticosteroids, immunomodulators, or high-dose anticoagulation along with high-dose corticosteroids or immunomodulators. A BILAG B disease activity score is moderate disease activity requiring low-dose oral corticosteroids, intramuscular or intra-articular corticosteroid injections, topical corticosteroids or immunomodulators, antimalarials, or symptomatic therapy. BILAG C corresponds to stable mild disease, BILAG D is inactive disease that was active previously, and BILAG E indicates the system was never involved.

8.1.2.4. 28 Tender Joint Count & 28 Swollen Joint Count

The 28 joints to be examined and assessed as tender or not tender for tender joint count and as swollen or not swollen for swollen joint count include 14 joints on each side of the patient's body: the 2 shoulders, the 2 elbows, the 2 wrists, the 10 metacarpophalangeal joints, the 2 interphalangeal joints of the thumb, the 8 proximal interphalangeal joints, and the 2 knees.

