8.1.2.5. Cutaneous Lupus Erythematosus Disease Area and Severity Index (CLASI)

The CLASI is a validated scale used to assess cutaneous manifestations of SLE consisting of 2 scores. The first summarizes the activity of the disease while the second is a measure of the damage done by the disease. Activity is scored on the basis of erythema, scale/hyperkeratosis, mucous membrane involvement, acute hair loss, and nonscarring alopecia. Damage is scored in terms of dyspigmentation and scarring, including scarring alopecia.

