9.2.2. Analysis Populations

Unless otherwise specified, the efficacy, health outcomes, and safety analyses will be conducted on the mITT population, defined as all randomized patients who received at least one dose of investigational product, even if the patient does not receive the correct treatment, or otherwise does not follow the protocol. Patients will be analyzed according to the treatment to which they were assigned. Significant protocol violations will be described in the SAP.

Safety analyses for the post-treatment Follow-up Period will be conducted on the follow-up population, defined as all randomized patients who received at least 1 dose of investigational product and have entered the post-treatment Follow-Up Period. Patients will be analyzed according to the dosing regimen to which they were assigned in the Treatment Period.

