9.2.4. Missing Data Imputation

The patients will be considered nonresponders for the NRI analysis if they do not meet the clinical response criteria (for example, remission of rash/arthritis, SRI-4) at Week 24. All nonresponders at Week 24 as well as all patients who discontinue study treatment at any time prior to Week 24, for any reason, will be defined as nonresponders for the NRI analysis for all categorical analyses at Week 24. Patients who require initiation or increase in dose of NSAIDs, corticosteroids, antimalarials, or immunosuppressants after randomization (as outlined in Section 6.8, Concomitant Therapy) will be analyzed as nonresponders from the day of initiation or increase in medication. Randomized patients without at least 1 postbaseline observation will also be defined as nonresponders for the NRI analysis. MMRM is the primary analysis method for analyzing the continuous efficacy endpoints. In this method no imputation is needed. However, a sensitivity analysis, the placebo multiple imputation (pMI) method will be used for

the selected analyses of the continuous endpoints at Visit 9 (Week 24). The pMI assumes that the statistical behavior of drug- and placebo-treated patients after discontinuing investigational product becomes that of placebo-treated patients.

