9.4. Primary and Secondary Analyses

9.4.1. Primary Analyses

The primary endpoint is the proportion of patients who achieve remission of arthritis and/or rash as defined by the SLEDAI-2K at Week 24. Either arthritis or rash (as defined by the SLEDAI-2K) are required to be present at baseline. If only arthritis is present at baseline, then arthritis has to be absent at Week 24 to meet the primary endpoint. If only rash is present at baseline, then rash has to be absent at Week 24 to meet the primary endpoint. If both arthritis and rash are present at baseline, then the primary endpoint is met if either arthritis, or rash, or both arthritis and rash are absent at Week 24.

Treatment comparison between baricitinib dose regimens (4-mg or 2-mg) and placebo in the proportion of patients achieving remission of arthritis and/or rash at Week 24 (Visit 9) will be analyzed using the logistic regression analysis with treatment and baseline disease activity (SLEDAI-2K <10 versus SLEDAI-2K \geq 10), baseline anti-dsDNA status (positive; negative), and region in the model. The proportions and 95% CI will be reported. Missing data will be imputed using the NRI method.

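### Do the two 50%-reduction responder rows in Table JAHH.4 wrongly count patients with a zero baseline as treatment failures?

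*Protocol*

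**What the plan says.** Table JAHH.4 sets out, for logistic regression, the proportion of patients with at least a 50% "reduction in number of joints affected by SLE arthritis at Week 12 and Week 24 compared to baseline", and a matching row for the CLASI activity score. Neither row limits the analysis to patients with a positive baseline. Other rows do carry a limit, for example "Change in anti-dsDNA level at Week 12 and Week 24 compared to baseline in patients with elevated anti-dsDNA at baseline"; the C3/C4 and corticosteroid-sparing rows are limited in the same way.

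Eligibility allows a single manifestation: "Have active arthritis and/or active rash as defined by the SLEDAI-2K at randomization" (Section 5.1.2, criterion [8]). The primary endpoint is built around this: "If only arthritis is present at baseline, then arthritis has to be absent at Week 24 to meet the primary endpoint" (Section 9.4.1), with a parallel rule for rash.

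Two general rules matter. Section 9.2.2: "Unless otherwise specified, the efficacy, health outcomes, and safety analyses will be conducted on the mITT population". Section 9.2.4: "The patients will be considered nonresponders for the NRI analysis if they do not meet the clinical response criteria", with remission and SRI-4 as its examples and Week 24 as its time point.

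The text introducing Table JAHH.4 says that the table summarises the exploratory analyses and that their details will be given in the SAP. Section 9.2 also assigns analysis details to the SAP. In Table JAHH.1 the corresponding exploratory endpoints are only generic: continuous and categorical measures derived from joint counts and from CLASI.

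**The concern.** A percentage reduction from zero is undefined. A rash-only patient may have no affected joints, and an arthritis-only patient may have a CLASI activity score of 0. If the two rows inherit the mITT default and the nonresponder rule is then applied, these patients become automatic failures in every arm. Each responder rate, and the difference between arms, would shrink by the share of patients able to respond. The analyses would understate the effect among patients who actually have the manifestation. Because neighbouring rows do state a baseline condition, its absence here looks like an oversight.

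**Working it through.** **1. Is the unfavourable reading fixed by the text?** It needs three steps: the rows state no population, so mITT applies; the nonresponder rule then applies; and an undefined percentage counts as failing the criterion.

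- The mITT default gives way where something else is specified, and Section 9.4.3 says that further specification of these analyses will be in the SAP.
- Section 9.2.4 concerns missing data and response criteria that can be evaluated. It does not address a percentage that cannot be computed. Treating such a patient as not evaluable fits the text as well as treating the patient as a nonresponder.
- The table does not define an affected joint (tender, swollen or both). Section 8.1.2.4 describes separate tender and swollen counts. The row is therefore not a full specification in other respects either.

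The document is silent on the point. It contains neither a wrong statement nor a contradiction.

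**2. The plan's own figure.** Section 9.1 gives about 81% power for the primary endpoint: 100 per arm, 40% versus 60%, two-sided 5%, chi-square. With p̄ the mean of the two rates,

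power = Φ{[(p₂ − p₁) − 1.96·√(2p̄(1 − p̄)/n)] / √([p₁(1 − p₁) + p₂(1 − p₂)]/n)}

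= Φ{(0.20 − 1.96 × 0.0707)/0.0693} = 81.2%. The figure reproduces, and the concern does not touch it.

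**3. Size on the unfavourable reading.** Let z be the share with a zero baseline. Kept as nonresponders: rates (1 − z)p with n = 100. Excluded: rates p with n = 100(1 − z). The 40% versus 60% among patients able to respond is an assumption borrowed from the primary endpoint.

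| z | Rates, all mITT | Difference (points) | Power, all mITT | Power, baseline above zero |
|---|---|---|---|---|
| 9% | 36.4% vs 54.6% | 18.2 | 73.7% | 77.4% (n = 91) |
| 10% | 36% vs 54% | 18 | 73% | 77% (n = 90) |
| 20% | 32% vs 48% | 16 | 64% | 72% (n = 80) |
| 30% | 28% vs 42% | 14 | 55% | 66% (n = 70) |

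With 30% versus 50%, excluding these patients gains about 3, 5 and 8 points of power at z = 10%, 20% and 30%. With 50% versus 70% it gains about 6, 12 and 16.

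**4. Which z is plausible?** The protocol does not give it. Section 4.3 reports, from earlier trials, arthritis in more than 80% of patients, rash in about 70%, alopecia in about 55% and mucosal ulcer in about 30%.

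- CLASI: absence of rash bounds z near 30%, but the score covers more than rash: "Activity is scored on the basis of erythema, scale/hyperkeratosis, mucous membrane involvement, acute hair loss, and nonscarring alopecia". Under independence, the share with none of rash, alopecia or ulcer is 0.30 × 0.45 × 0.70 = 9.45%. Requiring arthritis or rash, as this trial does, and taking arthritis at 80%, the arthritis-only share is 0.24/0.94 = 25.5%. Multiplying by 0.45 × 0.70 gives about 8%.
- Joints: absence of arthritis bounds z near 20%. The rash-only share under independence is 0.14/0.94 = 14.9%. The true share is probably lower, because a patient without SLEDAI-2K arthritis can still have a tender joint.

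These prevalences are SLEDAI items in other studies, so they are proxies only.

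**5. Validity.** Baseline status is fixed before dosing. With no treatment effect, the expected diluted rates are equal in all arms, because randomisation balances the zero-baseline share. The comparison loses sensitivity but gains no bias towards either dose.

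**The case for a change.** The strongest argument for the concern is the contrast within one table. The sponsor wrote baseline conditions for anti-dsDNA, C3/C4 and corticosteroid sparing, and tailored the primary endpoint to the manifestation present at entry. Only the two percentage-reduction rows, which need a positive baseline to be defined at all, lack one. A reader who applies the general defaults literally would keep everyone in. The remedy would be two short phrases on a pre-dose variable, and power is higher with the restriction in every scenario computed.

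Part of this stands. The rows carry no baseline condition, zero baselines are expected by design, and the arithmetic is sound. It is reasonable to check that the SAP states the denominator.

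The contrast proves less than it seems to. The conditions on the other three rows repeat the endpoint wording of Table JAHH.1, where the joint and CLASI endpoints were left generic. Nor is a cut-off just above zero the obvious answer: in a patient with one affected joint, any improvement is a 100% reduction, and a higher prespecified minimum is equally defensible. That choice is a design decision of the kind settled in a SAP.

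**Conclusion.** The concern does not hold. The protocol leaves the evaluable denominator of two exploratory responder variables unwritten, in a summary table whose details it assigns to the SAP. It does not state that zero-baseline patients are failures; that follows only by joining two general rules, neither of which deals with an undefined percentage. If the unfavourable reading were applied, the cost would be dilution. For CLASI at z = 9%, that is 1.8 points off an assumed 20-point difference and under 4 points of power, and more only if the zero-baseline share were nearer the 20% to 30% bounds. These sizes rest on assumed response rates, prevalences from other trials and independence between manifestations. The protocol claims no power for either variable and makes no multiplicity adjustment (Section 9.2.5). The primary and secondary analyses, the sample size and the safety analyses are unaffected. The SAP is not among the documents considered here, so whether it sets the denominator cannot be confirmed.

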4.1. Overview of Study Design

Study I4V-MC-JAHH (JAHH) is a Phase 2, multicenter, randomized, double-blind, placebo-controlled, parallel-group, outpatient, 24-week study evaluating the efficacy and safety of baricitinib 4-mg and 2-mg in patients with SLE receiving standard therapy.

Approximately 300 patients will be randomized 1:1:1 to receive baricitinib 4-mg daily, baricitinib 2-mg daily, or placebo (100 patients per treatment group). Patients will be stratified at randomization according to disease activity (SLEDAI-2K <10; SLEDAI-2K ≥10), anti-dsDNA status (positive; negative), and region (defined in the statistical analysis plan [SAP]).

The study consists of 3 periods:

[figure not shown]
- **Screening Period:** Patients meeting entry criteria begin the 3- to 42-day screening period by signing the informed consent form (ICF). Patients will be screened for study enrollment eligibility at Visit 1, and eligible patients will be randomized at Visit 2 (Week 0).
- **Double-Blinded Treatment Period:** Randomized patients begin the 24-week double-blind, placebo-controlled treatment period at Visit 2 (Week 0) and administer investigational product daily through Visit 9 (Week 24).

All patients will continue on stable background standard therapy consisting of corticosteroids, NSAIDs (for which the NSAID use is intended for treatment of signs and symptoms of SLE), a single antimalarial (such as hydroxychloroquine or chloroquine), and/or a single immunosuppressant (such as methotrexate [MTX], azathioprine, or mycophenolate). NSAID, antimalarial, and immunosuppressant doses should remain stable throughout the Double-Blinded Treatment Period. Decreases in corticosteroid dose, as well as subsequent increases to less than or equal to the baseline dose will be permitted between Week 0 and Week 16. No changes in corticosteroid dose (increases or decreases) will be permitted between Week 16 and Week 24. Further details regarding concomitant therapy are in Section 6.8.

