6.8. Concomitant Therapy

Patients will maintain their usual medication regimen for SLE and for any other concomitant diseases throughout the study unless specifically excluded in the protocol (see Section 5.2, Exclusion Criteria). Patients taking these medications should be on chronic stable doses at the time of randomization, as specified by the Entry Criteria (Section 5.2.1).

Concomitant SoC for SLE in this study can include corticosteroids, NSAIDs, a single antimalarial (such as chloroquine or hydroxychloroquine), and/or a single immunosuppressant (such as azathioprine, MTX, or mycophenolate).

Corticosteroid dose must be ≤ 20 -mg per day of prednisone (or equivalent) and stable for 2 weeks prior to randomization. Increases in corticosteroid dose are not permitted after randomization. Decreases in corticosteroid dose will be permitted between Week 0 and Week 16. If corticosteroid dose is decreased during this time period, subsequent increases, only to less than or equal to the baseline dose, will be permitted until Week 16. No changes in corticosteroids (increases or decreases) will be permitted between Week 16 and Week 24. Patients who require initiation or increase in dose of corticosteroids after randomization should be discontinued from investigational product, have an ETV, and proceed to the Follow-Up Period of the study.

Doses of NSAIDs (for which the NSAID use is intended for treatment of signs and symptoms of SLE), antimalarials, and immunosuppressants should not be adjusted during the Double-Blinded Treatment Period. Patients who require initiation or increase in dose of NSAIDs (for which the

NSAID use is intended for treatment of signs and symptoms of SLE), antimalarials, or immunosuppressants after randomization should be discontinued from investigational product, have an ETV, and proceed to the Follow-Up Period of the study.

Any changes to the patient's medication must be discussed with the investigator. Patients should be instructed to consult the investigator or other appropriate study personnel at the site before taking any new medications or supplements.

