Additional medications are to be avoided during the study unless required to treat an AE or for the treatment of an ongoing medical problem. If the need for concomitant medication arises, inclusion or continuation of the patient may be at the discretion of the investigator after consultation with Lilly or its designee. Any additional medication, whether prescription or over-the-counter, used at baseline and/or during the course of the study must be documented in the eCRF with start and stop dates.

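### Does the steroid-sparing endpoint wrongly shut out patients who first reach the dose threshold after Week 12?

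*Protocol*

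**What the plan says.** Table JAHH.1 (Protocol Section 3) and Table JAHH.4 (Section 9.4.3) define the endpoint in the same terms. The population is patients taking 10 mg/day of prednisone or more at baseline. Response is a reduction to 7.5 mg/day or less, held "for 12 consecutive weeks between Week 12 and Week 24". The endpoint is exploratory and is analysed by logistic regression.

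The dosing rules are elsewhere. Section 6.8 states: "Decreases in corticosteroid dose will be permitted between Week 0 and Week 16". After such a decrease, "subsequent increases, only to less than or equal to the baseline dose, will be permitted until Week 16". Section 4.1 then closes the dose: "No changes in corticosteroid dose (increases or decreases) will be permitted between Week 16 and Week 24". A patient who needs more than these rules allow is taken off investigational product and, under Section 9.2.4, "will be analyzed as nonresponders from the day of initiation or increase in medication".

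Section 9.4.3 leaves the detail of the exploratory analyses to the SAP, which was not available for this check. A note under Table JAHH.4 allows further methods, and Section 9.2 allows additional exploratory analyses.

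**The concern.** The endpoint fixes both a duration (12 weeks) and a window (Week 12 to Week 24), and the two have the same length. On nominal days there is no slack, so a responder has to be at the threshold by Week 12. Tapering stays open for another four weeks. A patient who lowers the dose as permitted at Week 14, and holds it to the end, falls in the same category as a patient who never tapered.

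If the two sets of rules were meant to fit together, the endpoint would be misclassifying some successful tapers and understating the response proportion. The stake would be one exploratory proportion in a subset of patients, not the main conclusions of the trial.

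**Working it through.** **Inputs.** Appendix 2 puts Week 12 at Day 85, Week 16 at Day 113 and Week 24 at Day 169, each with a tolerance of 4 days either way. The required duration and window come from Tables JAHH.1 and JAHH.4. The taper and fixed-dose periods come from Sections 4.1 and 6.8.

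**Step 1: the window.** 169 − 85 = 84 days, and 12 × 7 = 84 days. Nominal slack is 84 − 84 = 0. The observation behind the concern is correct.

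**Step 2: time left, by when the threshold is first reached** (169 minus the start day).

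| First at threshold | Start day | Days left | Weeks left | Meets 12 weeks |
|---|---|---|---|---|
| Week 12 | 85 | 84 | 12 | yes |
| Week 13 | 92 | 77 | 11 | no |
| Week 14 | 99 | 70 | 10 | no |
| Week 15 | 106 | 63 | 9 | no |
| Week 16 | 113 | 56 | 8 | no |

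The last 113 − 85 = 28 of the 113 − 1 = 112 taper days (28/112 = 25%) cannot contain a responder's first day at the threshold. That is a share of calendar time, not of patients. The protocol gives no basis for the share of patients.

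**Step 3: do the sections contradict each other?** Sections 4.1 and 6.8 govern what may be done to the dose and when. The endpoint tables govern what counts as sustained sparing. No section says that every permitted decrease must be able to earn a response. The ordinary reading of the tables is at or below the threshold throughout Weeks 12 to 24. On that reading each 'no' in the table above is a correct classification: the patient did not hold the reduction for 12 weeks.

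**Step 4: where the limit comes from.** Treatment ends at Week 24, so a 12-week run must start by 24 − 12 = Week 12 even with no window printed. The printed window does something else: it requires the run to be the final one. A patient at the threshold from Week 2 to Week 14 (14 − 2 = 12 weeks) who then goes back up, as the rules allow until Week 16, is not a responder. Window and duration together therefore describe a reduction maintained to the end of treatment.

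**Step 5: the boundary.** The zero slack depends on how days are counted. Counted inclusively, Day 86 to Day 169 is 169 − 86 + 1 = 84 days, so a Day 86 start would qualify. With actual visit dates, a Week 24 visit on Day 173 admits a start as late as 173 − 84 = Day 89, and the window itself runs from 165 − 89 = 76 to 173 − 81 = 92 days. These are dating conventions of the kind a protocol leaves to the SAP.

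**Step 6: the natural alternative.** A count of patients at the threshold by Week 16 and still there at Week 24 covers 169 − 113 = 56 days, or 8 weeks, all of it while dose changes are barred. The present 84 days split into 28 (Weeks 12 to 16) plus 56 (Weeks 16 to 24). The 28 days that would be dropped are the only part of the window in which a patient may go back up, to no more than the baseline dose, and stay on treatment.

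**Step 7: effect on power.** None can be derived. On assumed inputs that are not in the protocol (20% against 45%, 50 patients per arm, two-sided 5%), power is 77% with no loss of responders. If placebo loses 30% of its responders and active 10% (14.0% against 40.5%), it is 86%. If placebo loses 10% and active 30% (18.0% against 31.5%), it is 34%. Neither the direction nor the size follows from the documents.

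**The case for a change.** The best case for the concern is that the mismatch is visible on the page and is not a missing detail. Duration and window stand in two protocol tables, and no dating rule in the SAP can create more than a few days of slack without altering one of them. The protocol nowhere says that the threshold must be reached by Week 12, and specifying a 12-week run inside a 12-week window is an odd way to say throughout. The fixed-dose period from Week 16 to Week 24 offers a ready-made maintenance period that the endpoint does not line up with. Maintenance in that period is a real test, because a patient who needs an increase is withdrawn from treatment and counted as a nonresponder.

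The arithmetic in this stands, and so does the remark on wording: saying from Week 12 through Week 24 would be plainer. The inference does not. Calling late tapers uncounted responders presupposes a definition shorter than 12 weeks. Scoring a near miss like a complete failure is common to every dichotomised endpoint. Moving to Weeks 16 to 24 would gain the late tapers and lose both four weeks of duration and the stretch where a permitted re-increase can show that the reduction was not held. That is a choice between two reasonable definitions. A sponsor who wants the second count can add it as a further exploratory analysis under Sections 9.2 and 9.4.3 without touching the present endpoint.

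**Conclusion.** The concern does not hold. The day counts are right: 84 days required, 84 nominal days available, and 8 to under 12 weeks left for a patient who first reaches the threshold after Week 12 and by Week 16. They show a strict definition, not an erroneous one. The two tables that define the endpoint agree with each other and do not conflict with the dosing rules. The endpoint can be met by any eligible patient at the threshold from Week 12 to Week 24, and it applies identically to all three arms. No wrong figure, bias or power loss is demonstrated, and the primary and secondary endpoints and the sample size are not involved.

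This rests on reading the tables as requiring the reduction throughout Weeks 12 to 24, which is their ordinary sense, and on nominal visit days. Other day-counting conventions move the boundary by one to four days and do not alter the conclusion. No view is taken on the dose cut-offs or the taper rules.
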